Skin site (affected area "hot spot")	VLU: 5 cm above medial malleolus; DFU, site of previous ulcer	VLU: Infrared image of ant./lat./med/ gaitor area: DFU: plantar surface of foot	Identify the "hot spot" with thermography that will be targeted for home monitoring ²
Baseline temperature	No baselines were established for VLU or DFU "hot spots"	Baseline will be established by averaging the first 30 daily morning temperatures	Our R01 data of morning leg temperatures showed no statistically significant variation among temperatures taken 12 hours after treatment for 30 days ¹⁹
Frequency of temperature monitoring	VLU: Before and after cooling and 12 hours later (morning); DFU, daily (no specific time recommended)	Morning only	Standardized for this study; reduced effects of footwear and ambulation that could potential increase surface temperature on plantar region of foot ⁶¹
Skin temperature target	Cool if 4°F (2.2°C) above baseline	Cool if 2°F above baseline	By the time the tissue reaches 4°F, there is significant inflammation and tissue destruction ⁴¹
Population	Any VLU or DFU patient regardless of length of time to healing	Only those with previously healed chronic ulcers (≥ 12 weeks to heal)	Focus of RFA is on chronic ulcers; the emphasis for this study is prevention

D.4 Setting: The study will recruit participants from 5 major wound care centers and specialty practices (§ letters of support) within a 75-mile radius of Charleston, SC, as well as from one located in Greenville, NC. These centers and practices serve a large proportion of urban and rural residing, racially and ethnically diverse patients with leg and foot ulcers. The study will be conducted at the Research Nexus (CTSA) on the campus of the Medical University of South Carolina, at the Spartanburg Regional Healthcare System's Wound Healing Center, and at East Carolina University, NC.

D.5 Sample eligibility criteria: English speaking adults age 18 years-of-age or older with a healed VLU or DFU will be invited to participate (§Table 2).

TABLE 2: INCLUSION & EXCLUSION CRITERIA	
Inclusion for enrollment	Exclusion
Newly healed leg or diabetic foot ulcer within past six weeks	Open leg or foot ulcers
Ankle brachial index 0.8- 1.3mmHg (rule out absence of arterial disease)	Cognitive impairment: unable to recall 2 or more words or draw clock Mini-Cog™ (0.84) for cognitive impairment ⁶²

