The primary efficacy outcomes are recurrence of ulcers, both venous leg ulcers and diabetic foot ulcers, since enrollment into the study (categorical), and changes in pain, quality of life and physical activity from baseline to the three subsequent visits at 1, 3, and 6 months post-baseline (continuous). In primary analysis we will compare differences in proportions of participants developing a VLU/DFU over the entire study period between the cooling pack and placebo groups using chi-square analysis. We will obtain odds ratios for the categorical outcome measure recurrence of VLU/DFU adjusted for putative covariates such as demographic (age, gender, race/ethnicity, marital status, job category and area of residence) and clinical (time since last ulcer, and wearing compression stockings or footwear [yes/no]) characteristics using logistic regression modeling (LRM). Modeling will be carried out in a sequential fashion. For example a first model will contain recurrence of VLU/DFU (yes/no) as response variable, treatment (cooling vs, placebo) as primary variable of interest and time since last ulcer as adjustment variable. The model will be further adjusted using sets of putative predictive covariates such as demographic and clinical characteristics as well as secondary outcomes pain, quality of life and physical activity (step counts). We will examine effect modifications of covariates through inclusion of a covariate-by-treatment interaction term in the multivariable models. Analyses will be repeated within the ulcer subgroups (VLU and DFU) as appropriate.

Survival distributions for recurrence of VLU/DFU will be obtained for each group using the Kaplan-Meier

product limit method, and will be compared using the logrank test 63, 64, 65. Cox proportional hazards regression modeling (PHM) will be used with time since last ulcer to recurrence of new ulcer as the dependent variable and treatment (cooling vs. placebo) as the primary independent variable. Additional covariables and interaction terms will be added as described above for LRM analyses.

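### The Cox model's clock starts at the last ulcer, before randomisation, and the model also adjusts for time since last ulcer: that covariate's effect is biased towards protection, while the treatment comparison is essentially intact.

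*Combined protocol and SAP*

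**What the plan says.** All the analysis text is in D.9, Analysis plan for Aim 1.

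- The categorical primary outcome is "recurrence of ulcers, both venous leg ulcers and diabetic foot ulcers, since enrollment into the study (categorical"), so its origin is enrollment. It is compared by chi-square over the study period.
- The Cox model uses "time since last ulcer to recurrence of new ulcer as the dependent variable", with "treatment (cooling vs. placebo) as the primary independent variable".
- On further Cox terms: "Additional covariables and interaction terms will be added as described above for LRM analyses".
- The first of those logistic models has treatment "as primary variable of interest and time since last ulcer as adjustment variable", and the same variable is listed again among the clinical covariates: "clinical (time since last ulcer, and wearing compression stockings or footwear [yes/no]) characteristics".
- No origin is given for the Kaplan-Meier curves or the logrank test, and delayed entry (left truncation) is not mentioned.

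Eligibility fixes what happens before entry. Table 2 (D.5) admits a "Newly healed leg or diabetic foot ulcer within past six weeks" and excludes anyone with an open ulcer. D.1 and Table 1 restrict the trial to ulcers that took about 12 weeks or more to heal. The plan does not say whether the last ulcer is dated from its onset or from its healing.

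**The concern.** The two analyses of recurrence count time from different origins. On the Cox clock, each participant contributes an interval before enrollment in which no event can occur, because a person with an open ulcer is not enrolled. That interval is 0 to 6 weeks if the clock starts at healing. It is longer by the healing period if the clock starts at onset.

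Unless participants enter the risk set at randomisation, early risk sets contain people who have not yet enrolled and cannot fail. Those with longer gaps are held event-free for longer. When the gap is also a covariate, it is part of the response and a predictor of it, so a longer gap looks protective even if it has no effect.

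At stake are the coefficient for time since last ulcer, possibly its planned interaction with treatment, and any absolute risk read on that clock. The trial could report that a longer interval since the last ulcer protects the skin when the time scale has produced that result.

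**Working it through.** **Inputs from the plan.** Six months of follow-up (D.1); 90 per group, odds ratio 3.0, two-sided alpha 0.05, 25% inflation for dropout (D.8); entry within six weeks of healing (Table 2); at least 12 weeks to heal (Table 1).

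**The plan's own figure.** D.8 gives no events, hazard ratio or power for the Cox model, only power above 90% for the continuity-corrected chi-square test. Its printed rates are 25% in both groups, which cannot give an odds ratio of 3.0. With 25% under cooling, that odds ratio implies placebo odds of 3 × 0.25/0.75 = 1, a risk of 50%. Power at 90 per group is then 91.9%, which reproduces the claim. I use 50% v 25%. Under constant hazards the true hazard ratio is ln(0.75)/ln(0.50) = 0.415.

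**Mechanism.** Let L be the gap before entry and T the time from entry to recurrence, with L unrelated to T and T having constant hazard λ. The plan's response is Y = L + T. The hazard at Y = y is zero for y < L and λ afterwards, so a larger L means a lower hazard at early y. With L between 0 and 6 weeks, only risk sets in the first six weeks of the clock are affected, because everyone has entered after that.

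**Simulation.** 90 per arm, 26 weeks, 25% random dropout, 600 trials per scenario, and a covariate L with no true effect. The distributions of L are assumptions: uniform on 0–6 weeks for a healing origin, and 12–30 weeks as a narrow onset origin. *As written* means a clock from the last ulcer, no delayed entry, and adjustment for L. All models in the table adjust for L.

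| Placebo v cooling risk; gap | Model | Treatment HR | Treatment rejections | HR per week of L | False rejections for L |
|---|---|---|---|---|---|
| 50% v 25%; 0–6 wk | As written | 0.411 | 90.5% | 0.947 | 9.3% |
| | From randomisation | 0.412 | 90.2% | 1.004 | 5.7% |
| | Delayed entry | 0.412 | 90.3% | 1.003 | 3.7% |
| 50% v 50%; 0–6 wk | As written | 0.987 | 4.7% | 0.938 | 16.7% |
| | From randomisation | 0.987 | 4.7% | 0.999 | 6.2% |
| | Delayed entry | 0.987 | 4.3% | 0.998 | 5.5% |
| 50% v 25%; 12–30 wk | As written | 0.398 | 92.5% | 0.941 | 60.5% |
| | From randomisation | 0.402 | 92.8% | 1.000 | 4.3% |
| | Delayed entry | 0.402 | 92.5% | 1.000 | 6.0% |

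**Covariate.** Across four pairs of event rates with the 0–6 week gap and constant hazard, the spurious hazard ratio is 0.938 to 0.951 per week. Per month of 4.35 weeks, that is 0.938^4.35 = 0.76 to 0.951^4.35 = 0.80. False rejection is 7 to 17%; a separate 300-trial run at 50% v 25% gave 12%. With onset 3–12 months before healing, the hazard ratio is 0.72 per month and every trial rejects.

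If the hazard truly falls with time since healing (Weibull shape 0.6), a clock from randomisation shows a real association of 0.94 to 0.95 per week. The model as written exaggerates it to 0.89 to 0.91.

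**Event-free person-time.** About 13 to 16% of analysed time with the 0–6 week gap, and 54 to 56% with 12–30 weeks.

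**Treatment.** Type I error of the as-written clock, adjusted or not, is 3.5 to 5.2% in every null scenario. Dilution needs three things together: an onset origin, a widely varying gap, and no adjustment for it. With a lognormal gap of median 6 months:

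- log-SD 0.6: HR 0.415 becomes 0.444 and power 89% becomes 81%; with adjustment, 0.404 and 88%.
- log-SD 0.8: HR 0.411 becomes 0.453 and power 90% becomes 83%; with adjustment, 0.399 and 90.5%.

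With the narrower 12–30 week gap, the unadjusted model moves only from 0.403 to 0.408, and power from 92.8% to 91.7%.

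**Early absolute risk, if read on this clock.** In months, with a constant hazard giving 50% at six months, placebo risk at day 28 (0.92 months) after randomisation is 1 − 0.5^(0.92/6) = 10.1%. With a uniform gap of 0 to 1.4 months added to each time, the apparent risk is 3.4%.

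**The case against.** The strongest reply is that the answer the trial exists to give is unaffected. Treatment is the variable of interest, randomisation balances the gap between arms, and the primary analysis is a chi-square test that does not use this clock. All of that stands.

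It also stands that healing is the more natural origin in a trial of newly healed skin. On that reading the spurious covariate effect would reach significance in only about one trial in ten at the design rates. The largest figures rest on onset gaps that I assumed, since the documents give only a minimum healing time. No aim or benchmark concerns this covariate.

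Three stronger readings are tempting, and the documents do not support them:

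- **The treatment effect is biased or loses power.** This happens only in an onset-origin model with widely varying gaps that leaves the gap out. The spurious covariate effect needs the gap put in. A single fitted model does not show both.
- **The Kaplan-Meier curves will understate early risk threefold.** The plan gives them no origin. The 3.4% against 10.1% applies only if they inherit the Cox clock.
- **The plan rules out delayed entry.** It is silent, and time since healing with left truncation would be a sound choice.

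What remains is that the written rule, followed literally, gives a wrong coefficient for a covariate the plan names first and proposes to examine for interaction.

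**Conclusion.** The point holds as a flaw in a supporting analysis. Followed as written, and without delayed entry, the Cox model biases the coefficient for time since last ulcer towards protection. Under constant hazard the spurious hazard ratio is about 0.76 to 0.80 per month for a 0–6 week gap. False significance then rises from a nominal 5% to 7–17%, and much further if the clock starts at ulcer onset. Any absolute risk read on that clock is too low early on.

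The treatment comparison is sound in type I error. Its hazard ratio and power are essentially unchanged with a healing origin or after adjustment for the gap. In the exceptional case (onset origin, wide gaps, no adjustment) the hazard ratio rises by 0.03 to 0.04 and power falls by 7 to 8 points.

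These sizes rest on assumed gap distributions, on 50% v 25% six-month risks inferred from the odds ratio, on 180 participants, and on the absence of left truncation. Covariate-by-treatment interactions were not simulated.

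**What to change.** Define the last ulcer as the index ulcer, dated at healing, and state one origin for all time-to-event analyses. Either:

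1. Measure Cox, Kaplan-Meier and logrank times from randomisation, and keep time from healing to randomisation as a baseline covariate. This matches the origin of the categorical outcome and is the simpler choice.
2. If time since healing is wanted as the scale, let participants enter the risk set at randomisation (left truncation) in all three analyses, and drop time since last ulcer from the Cox covariates, because the time scale then carries it. In the simulations, keeping it did no harm under delayed entry.

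The cost is one or two sentences in the analysis plan. No new data should be needed: the six-week eligibility rule already depends on the healing date, and E.2.a has the enrollment date recorded. Sample size and the primary test do not change.

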Benchmarks for success: Although it is difficult to precisely predict the effect of cooling on ulcer incidence during the study in these two groups, we view a 50% reduction in the incidence of a leg ulcer in the cooling pack group compared to placebo 7,9.

Impact on pain, physical activity and quality of life – pain will be assessed using a visual analog scale (0.99 interrater reliability) 63 and the Brief Pain Inventory (Cronbach's 0.88) 64, physical activity with an accelerometer (Basis Smart Watch, Basis Science, Inc., San Francisco), a user-friendly activity monitor <http://www.mybasis.com/> and International Physical Activity Questionnaire (IPAQ) (pooled Spearman R 0.81) 65, and quality of life with the VEINES QOL/sym Questionnaire (internal consistency 0.87; test-retest reliability 0.86) 66, the Neuropathic Pain Questionnaire (NPQ) (internal consistency 0.82), the Geriatric Depression Scale, and the SF-12 Health Survey. The VEINES will be administered to the VLU participant population and the NPQ to the DFU participant population. While we recognize that wrist monitors may not be the most accurate in terms of energy expenditure, we are working with an atypical population where hip or bicep-type accelerometer sensors found in (i.e., Bodymedia Fit, and Fitbit Zip), may not be feasible. Thus, we have selected a wrist accelerometer based on data that suggest this design may be better suited for chronic populations; results revealed acceptable agreement between the Basis watch and indirect calorimetry found in hip sensors 67. Basis captures resting movements, is less easy to misplace/lose than hip accelerometers, has multiple-sized wrist bands, and numerous programmability options. These three outcomes will be assessed at baseline, and months 1, 3 and 6. **Benchmarks for success:** Compared to the placebo group, the cooling pack group will have lower pain scores (lower VAS and IPAQ scores), increased physical activity (e.g., more steps taken and participates more frequently in activities, and higher ratings on the SF-12), and improved quality of life (higher ratings on VEINES or NPQ, and GDS).

Analysis plan for Aim 1

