In analysis of the continuous efficacy outcome measures, we will compare unadjusted mean differences in pain and quality of life total scores from baseline to 1, 3 and 6 months via paired t-tests (or equivalently non-parametric Wilcoxon Signed-rank test) between the (cooling vs. placebo) groups. We will use a general linear models (GLM) approach to compare mean differences for the change from baseline outcome measures adjusted for putative predictive covariables. Modeling will be carried out in a sequential fashion for each outcome variable individually analogous to the modeling described above. Using quality of life as example, the first model will contain change in quality of life from baseline to 6 months as response variable, treatment (cooling vs. placebo) as primary variable of interest and baseline quality of life as adjustment variable. This procedure will be repeated for pain measures as well as the accelerometer step counts/physical activities. For the accelerometer, baseline will be established by averaging the first 30 daily step counts/activities; change from baseline will be assessed at 6 months as described above.

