Baseline visit - demographic information (i.e., age, race, gender, co-morbid conditions, body mass index, number of previous ulcers, length of healing time, location, medications taken) and questionnaires on pain, physical activity and quality of life will be collected, affected leg or foot skin at the site of the newly healed ulcer to identify the “hot spot” will be imaged, procedural instructions for using the accelerometer given, protocol for self monitoring of temperature and self management of temperature elevation will be shown via DVD and written instructions given, and a test will be administered to assess understanding. Similar to our other studies, we will produce a YouTube video and take-home DVD of these instructions for standardization. Supplies include: thermometer, pack and freezer bag (given by Research Nexus staff after the research assistant has completed all study procedures) to be kept in freezer at all times except during treatment, a freezer thermometer to ensure temperatures are kept at 0°F, skin marker, study logs and clipboard with attached pen for recording daily temperatures/maintenance and bolus cooling (times, dates)/freezer temperature, and timer (for 30 minutes of cooling). Baseline questionnaires to be administered include: VAS, BPI, IPAQ, SF-12, GDS, and the VEINES QoL or NPQ (as applicable).

Visit 1 – (month 1) - the daily month 1 temperature readings taken over 28 – 31 days (depending on the month) with the thermometer will be downloaded using a software program and averaged to establish the mean skin temperature. These data will be recorded in REDCap. The infrared thermometer will be programmed to sound an alarm when the readings are 2°F above the mean. Also at this visit the skin site will be imaged with the infrared camera and uploaded for comparison against the baseline reading. Data will also be uploaded from the accelerometer to assess physical activity. Any changes in demographics such as taking new medications will be evaluated, and the pain scales will be administered. Process measures will be collected including ease of use of thermometer, problems with study procedures, and fidelity to self-monitoring assessed (e.g., through downloaded temperature readings). Visit 1 questionnaires to be administered include: VAS, BPI, IPAQ, and the VEINES QoL or NPQ (as applicable).

Visit 2 – (month 3) – the daily months 2 and 3 temperature measurements and accelerometer
Version 10.0 07/23/18

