information will be downloaded, the skin site imaged, and demographic (i.e., changes in co-morbid conditions, new medications taken) and pain questionnaires administered. Process measures will be collected. Visit 2 questionnaires to be administered include: VAS, BPI, IPAQ, and the VEINES Qol or NPQ (as applicable).

Visit 3 – (month 6 final visit) – the daily months 4 – 6 temperature measurements and accelerometer information will be downloaded, the skin site imaged, demographic, pain and quality of life questionnaires administered. Process measures will be collected. Visit 3 questionnaires to be administered include: VAS, BPI, IPAQ, SF-12, GDS, and the VEINES Qol or NPQ (as applicable). During this final visit, an exit satisfaction survey interview will be conducted to ascertain information about overall feasibility, problems encountered, satisfaction, recommendations for changes to procedures, likelihood of maintaining/sustaining.

Ongoing supportive phone calls: Calls will be made to both groups 24 hours after the start of the study, weekly during weeks 1 – 4, and then monthly by research assistants. We will provide reinforcement of study procedures, solicit information about problems encountered, adherence, side effects, and leg temperatures and answer any questions (§Table 4).

Study staff: We will elicit feedback using a rating scale we have developed for our ongoing R01 that assesses the perceptions of staff, their beliefs regarding the sustainability of the intervention, likelihood of implementation into practice, and dissemination potential.

Relevant literature in support of or in disagreement with the potential results on pain:

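### By the visit lists, no quality-of-life score is common to both ulcer types at months 1 and 3, and the 85% power is expressed on a scale that only about half the sample receives

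*Combined protocol and SAP*

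**What the plan says.** **Planned comparison.** The Analysis plan for Aim 1 (D.9) lists change in quality of life at months 1, 3 and 6 among the primary efficacy outcomes. For the continuous outcomes, "we will compare unadjusted mean differences in pain and quality of life total scores from baseline to 1, 3 and 6 months", with treatment arm as the contrast. It then describes a mixed model with quality of life as the dependent variable and a time-by-treatment term. The example of an adjusted model uses change from baseline to month 6.

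**Instruments.** Outcome measures for Aim 1 (D.9) names VEINES under quality of life, together with "the Neuropathic Pain Questionnaire (NPQ) (internal consistency 0.82), the Geriatric Depression Scale, and the SF-12 Health Survey". It continues: "The VEINES will be administered to the VLU participant population and the NPQ to the DFU participant population". Of pain, physical activity and quality of life it says "These three outcomes will be assessed at baseline, and months 1, 3 and 6".

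**Visit lists (D.9, Data collection time points).**
- Baseline: "Baseline questionnaires to be administered include: VAS, BPI, IPAQ, SF-12, GDS, and the VEINES QoL or NPQ (as applicable".
- Month 1: "Visit 1 questionnaires to be administered include: VAS, BPI, IPAQ, and the VEINES QoL or NPQ (as applicable".
- Month 3: "Visit 2 questionnaires to be administered include: VAS, BPI, IPAQ, and the VEINES Qol or NPQ (as applicable".
- Month 6: "Visit 3 questionnaires to be administered include: VAS, BPI, IPAQ, SF-12, GDS, and the VEINES Qol or NPQ (as applicable".

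**GDS elsewhere.** Section E.1 has GDS completed at every study visit.

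**Power.** Section D.8 claims 85% power for 0.45 SD in the continuous outcomes (two-sided alpha 0.05, independent-samples t-test). It translates this into 1.3 VEINES units with an SD of 2.8.

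**The concern.** A comparison of cooling with placebo over all participants needs one score that everyone has. By the visit lists, two of the three planned follow-up times have none: VLU participants have VEINES, DFU participants have NPQ, and neither group has SF-12. The longitudinal model uses the same visits and has the same gap.

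The plan does not say which instrument supplies the total score, and it gives no rule for using VEINES and NPQ together. The choice would therefore fall to the analyst after data exist, for an outcome labelled primary efficacy. If the two were put into one column, the estimate would mix a venous quality-of-life scale with a neuropathic pain scale and would have no interpretable unit.

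The power statement has a related weakness. It takes the full sample size but is expressed on a scale that only VLU participants complete.

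**Working it through.** **1. Who has which score, and when** (D.9, visit lists)

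| Visit | SF-12 | GDS | VEINES | NPQ |
|---|---|---|---|---|
| Baseline | all | all | VLU | DFU |
| Month 1 | not listed | not listed (E.1: all) | VLU | DFU |
| Month 3 | not listed | not listed (E.1: all) | VLU | DFU |
| Month 6 | all | all | VLU | DFU |

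The only candidate for a common score at months 1 and 3 is GDS, and only if E.1 overrides the visit lists. It is a depression scale. Its direction is also inconsistent: the D.9 benchmark counts higher GDS ratings as improved quality of life, while E.1 treats totals above 5 as suggestive of depression. The same benchmark places SF-12 under physical activity, so even at month 6 the plan does not designate a common quality-of-life score.

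**2. Reproduce the stated power**

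Inputs from D.8: d = 0.45, n = 90 per arm, two-sided alpha 0.05.

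Normal approximation: power ≈ Φ(d·√(n/2) − 1.960).

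- n = 90: 0.45 × √45 = 3.019; Φ(1.059) = 85.5%. The noncentral t gives 85.1%.
- Raw effect: 0.45 × 2.8 = 1.26, stated as 1.3.

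The 85% reproduces, provided that all 90 per arm have the scale.

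**3. Power for VEINES**

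Sections A and E.1.a give 90 VLU and 90 DFU participants. Assuming a 1:1 split within type, VEINES is available for 90/2 = 45 per arm. D.8 also gives 240 randomised; assuming equal ulcer types and arms, that is 240/4 = 60 per arm.

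- n = 45: 0.45 × √22.5 = 2.135; Φ(0.175) = 56.9%. The t distribution gives 56.0%.
- n = 60: 0.45 × √30 = 2.465; Φ(0.505) = 69.3%. The t distribution gives 68.6%.
- With the rounded effect, 1.3/2.8 = 0.464 SD, n = 45 gives 58.6% (t).

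**4. Difference detectable with 85% power**

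(1.960 + 1.036) × √(2/n):

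- n = 45: 2.996 × 0.2108 = 0.63 SD, or 0.63 × 2.8 ≈ 1.8 VEINES units.
- n = 60: 2.996 × 0.1826 = 0.55 SD, or 0.55 × 2.8 ≈ 1.5 VEINES units.

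Both exceed the stated 1.3 units.

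**The case against.** The strongest reply is that the plan never says VEINES and NPQ will be combined. It refers to scores in the plural, models each outcome variable separately, assigns the two instruments by ulcer type, and says analyses will be repeated within VLU and DFU. On that reading each instrument is analysed in its own group. This stands in part: a reader might infer that the plan instructs the two scales to be merged, and no text does so. However, the by-type sentence follows the recurrence models and describes repeats of an overall analysis. The continuous comparisons are framed by arm, and ulcer type is not among the listed covariates. If analysis within type is intended, the plan should say so, and the 85% power does not apply to it.

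A reader might also infer that no overall quality-of-life comparison is possible at all. The documents do not support that. SF-12 and GDS are listed for everyone at month 6, which is the endpoint of the example adjusted model, and 85% for 0.45 SD still reproduces there with 90 per arm. VEINES and NPQ can be compared within type at every visit.

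The visit lists may not be exhaustive, since they are worded as inclusive and omit GDS where E.1 requires it. But SF-12 is named at baseline and month 6, so its absence at months 1 and 3 looks deliberate. The accompanying text for those two visits also mentions pain questionnaires but not quality of life. That conflicts with the assessment times in Outcome measures for Aim 1.

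Finally, participants who ulcerate are withdrawn, so those withdrawn before month 6 have no scheduled SF-12 after baseline. It is tempting to count that here. It is a separate issue: it arises from the withdrawal rule, the plan offers multiple imputation for end-of-study values, and an excess of withdrawals on placebo is the trial's hypothesis rather than a known fact. Extra SF-12 visits would address it only partly.

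**Conclusion.** The point holds for months 1 and 3 and for the longitudinal model. As scheduled in the visit lists, neither has a quality-of-life score common to both ulcer types, and the plan does not name the score to be used. GDS cannot be relied on to fill the gap until its schedule and direction are reconciled, and even then it measures depression. The month 6 comparison on SF-12 and the within-type comparisons are not affected.

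The stated 85% power is correct for a scale given to all 90 per arm. For VEINES, the scale on which it is expressed, power for 0.45 SD is about 56% with 45 per arm and about 69% with 60 per arm. These figures assume equal splits by arm within type (and equal ulcer types for the 240) and a score for every participant counted. Missing scores would lower them. The width of the range reflects the protocol's two sample sizes, 180 and 240.

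**What to change.** 1. Name SF-12, or another measure common to both ulcer types, as the overall quality-of-life outcome, and add it to the month 1 and month 3 visits. For SF-12 the cost is a 12-item form at two existing visits, a few minutes of participant time each. If the visit lists stay as they are, restrict the overall quality-of-life comparison to month 6.
2. State that VEINES is analysed within VLU only and NPQ within DFU only, and that the two are never combined into one score.
3. Reconcile the GDS schedule and scoring direction across Outcome measures for Aim 1, the visit lists and E.1.
4. Restate the quality-of-life power in D.8 for the sample that has the score: 85% for a scale given to all 90 per arm, and about 56% to 69% for VEINES, depending on which sample size applies.

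Items 2 to 4 are changes of wording only.
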